8 ASSESSMENT OF EFFICACY

Assessment of efficacy includes careful evaluation of blood, lymph nodes and bone marrow by medical history, physical examination, laboratory tests (e.g. CBC and differential count), bone marrow aspirate and/or biopsy (as applicable) and CT scans of neck/chest/abdomen/pelvis, as applicable. Investigator assessed efficacy response will be considered in the study.

8.1 Specification of the Efficacy Parameters

- **ORR** is defined as sum of CR and PR rates as defined by iwCLL guideline for CLL (Hallek *et al.* 2018) [12]. Only those patients who have had a pre-treatment baseline efficacy evaluation and at least one post-treatment efficacy evaluation (that includes confirmed disease progression) will be considered evaluable for response.
- **CR rate** will be assessed by the investigator according to the iwCLL guideline for CLL. Only those patients who have had a pre-treatment baseline efficacy evaluation and at least one post-treatment efficacy evaluation (that includes confirmed disease progression) will be considered evaluable for response.
- **PFS** is defined as time of the first dose of Tenalisib to disease progression or death. Subjects who die without a reported prior progression will be considered to have progressed on the date of their death. Subjects who did not progress or die will be censored on the date of their last tumor assessment.
- **DoR** is defined as the time when the measurement criteria are first met for PR or CR (whichever is reported first) until the date of documented disease progression or death. For subjects who neither progress nor die, the duration of response will be censored at the date of their last disease assessment.
- **Best Overall Response:** The best overall response is the best response, as assessed and confirmed by site PI, from the start of the treatment until disease progression or discontinuation from the study.

Disease parameters:

- Measurable lesions: Measurable lesions are defined as those that can be accurately measured in at least two dimensions with conventional techniques with size ≥ 1.5 cm. All tumor measurements should be recorded in centimeters.
- Non-measurable lesions (evaluable disease): All other lesions including small lesions (>1 cm) are considered non-measurable disease. Bone lesions, leptomeningeal disease, ascites, pleural/pericardial effusions, lymphangitis, and cystic lesions are all non-measurable.
- Target lesions: All measurable lesions up to a maximum of 6 lesions total, representative of all involved organs, should be identified as target lesions and recorded and measured at baseline. Target lesions should be selected on the basis of their size (lesions with the longest SPD diameter), and the highest SUV avidity (high SUV lesions may be prioritized even if not the largest lesions, and their suitability for accurate repeated measurements (either by imaging techniques or clinically). A baseline sum of the diameters (longest for non-nodal lesions, short axis for nodal lesions) for all target lesions will be calculated and reported as the baseline sum

CONFIDENTIAL Page 48 of 61

diameters. The baseline sum of the diameters will be used as reference to further characterize any objective tumor regression in the measurable dimension of the disease.

• Non-target lesions: All other lesions (or sites of disease) including any measurable lesions over and above the 6 target lesions should be identified as non-target lesions and should also be recorded at baseline. Measurements of these lesions are not required, but the presence, absence, or in rare cases unequivocal progression of each should be noted throughout follow-up.

8.2 Response Evaluations and Measurements

Disease response assessments should be performed at C3D1 (\pm 7 days), C5D1 (\pm 7 days) and C8D1 (\pm 7 days), and/ or at the EOT or as clinically indicated (if clinical progression is suspected). If CT scan at Screening is negative for disease involvement in the neck, subsequent CT scans may not include neck. If CT scan at Screening is positive for disease involvement of the neck, subsequent CT scans must include neck. Disease assessment will be performed as per iwCLL guideline for CLL (Hallek *et al.* 2018) [12].

To define the response to treatment, 2 groups of parameters will be assessed and documented:

- Group A parameters: assess the lymphoid tumor load and constitutional symptoms.
- Group B parameters: assess the hematopoietic system (*Table 6*).

For complete remission (CR), all criteria given below should be met. For progressive disease, at least 1 of the criteria of group A or group B should be met; For partial remission, at least 2 of the parameters of group A and 1 parameter of group B need to improve if previously abnormal; if only 1 parameter of both groups A and B is abnormal before therapy, only 1 needs to improve.; For stable disease, all of the criteria have to be met; constitutional symptoms alone do not define PD.

Table 6: Response Criteria for CLL (iwCLL) (Hallek et al, 2018)

Group	Parameter	CR	PR	PD	SD
A	Lymph nodes	None ≥ 1.5 cm	Decrease ≥ 50% (from baseline) *	Increase ≥ 50% from baseline or from response	Change of -49% to +49%
	Liver and/or spleen size\$	Spleen size <13 cm; liver size normal	Decrease ≥ 50% (from baseline)	Increase ≥ 50% from baseline or from response	Change of -49% to +49%
	Constitutional symptoms	None	Any	Any	Any
	Circulating lymphocyte count	Normal	Decrease ≥ 50% from baseline	Increase ≥ 50% over baseline	Change of -49% to +49%
В	Platelet count	≥ 100 x 10 ⁹ /L	≥ 100 x 10 ⁹ /L or increase ≥ 50% over baseline	Decrease of ≥ 50% over baseline secondary to CLL	Change of -49% to +49%
	Hemoglobin	≥ 11.0 g/dL (untransfused and without erythropoietin)	≥ 11.0 g/dL or increase ≥ 50% over baseline	Decrease of ≥ 50% over baseline secondary to CLL	Increase <11.0 g/dL or <50% over baseline, or

CONFIDENTIAL Page 49 of 61

Version: 1.0, Dated 12 September 2019

				decrease <2 g/dL
Marrow	Normocellular, no CLL cells, no B-lymphoid nodules	Presence of CLL cells, or of B- lymphoid nodules, or not done	Increase of CLL cells by ≥ 50% on successive biopsies	No change in marrow infiltrate

[§]spleen size is considered normal if <13cm. There is no firmly established international consensus of the size of a normal liver; therefore, liver size should be evaluated by imaging and manual palpation and be recorded in CRF.

Note: Certain therapies (e.g., kinase inhibitors) may cause lymphocytosis. In the setting of therapy with such agents, an increase in blood lymphocyte count by itself does not uniformly indicate an increased tumor burden but may reflect redistribution of leukemia cells from lymphoid tissues to the blood [12]. As Tenalisib is a kinase inhibitor, increased lymphocytosis alone will not be considered a sign of treatment failure or PD in this study.

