5.2 Concomitant Medications

In general, patients should not to take any concomitant medications during the study, unless it is required as a standard of care (as necessary supportive care), prophylaxis or for the treatment of adverse event in the opinion of the treating investigator. The following guidance should be followed for concomitant medications and the information including blood transfusion should be recorded in CRF.

 Antimicrobial and/or anti-viral prophylaxis should be used according to local standard practice; PJP and herpes zoster prophylaxis is strongly recommended. CMV carriers will be monitored per institutional guidelines and/or will be given anti-CMV therapy (e.g.,

Version: 1.0, Dated 12 September 2019

- ganciclovir, valganciclovir). Similarly, chronic carriers of HBV should receive prophylactic anti-viral therapy.
- G-CSF and other hematopoietic growth factors may be used for the management of acute toxicity (such as febrile neutropenia) when clinically indicated.
- Transfusions (blood/platelets) may be given, based on standard criteria and clinical judgment.
- No routine prophylactic anti-emetics or pre-medications should be given outside of protocol requirements. However, these medications may be administered for the treatment of symptoms.
- Patient may receive prophylactic allopurinol, in case the risk of tumor lysis syndrome.
- Low doses of steroids are allowed if it administered at dose ≤ 20 mg per day of prednisone or equivalent. The dose should be stabilized for at least 1 week or 5 halflives (whichever is shorter) prior to C1D1.
- Patients are permitted to use of topical, ocular, intra-articular, intranasal, and inhaled corticosteroids (with minimal systemic absorption).
- Inactivated seasonal influenza vaccine can be given to subjects before treatment and while on therapy without restriction.
- If concomitant treatment of drugs metabolized by CYP3A4/CYP2C9 enzymes are clinically warranted, careful observation of the patient is advised.
- Low molecular weight heparin (LMWH), Dabigatran or Edoxaban is acceptable for prophylaxis and/or treatment of venous thrombosis.

5.3 **Prohibited Medications**

The following treatments are prohibited while on the clinical trial and should be discontinued:

- Any other anti- leukemia/lymphoma therapy
- Herbal medications. Patients should stop using herbal medications at least 7 days prior to C1D1.

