6.2.3 Medical history

Comprehensive medical history should be taken at least for period of minimum 6 months by the investigator/qualified designee. In addition, information on cytogenetics and immunophenotyping, if available at the screening will be noted. Investigator should note at least 1 of the following criteria to document active disease that warrants initiation of therapy;

- a. Evidence of progressive bone marrow failure as manifested by the onset or worsening of anemia (Hb <10 g/dL) and/or thrombocytopenia (count <100 X 10⁹/L), OR
- b. Massive (lower edge of spleen ≥ 6 cm below the left costal margin) progressive, or symptomatic splenomegaly, OR
- c. Massive nodes (≥ 10 cm in the longest diameter), progressive, or symptomatic lymphadenopathy, OR
- d. Progressive lymphocytosis in the absence of infection, with an increase in blood absolute lymphocyte count (ALC) >50% over a 2-month period or lymphocyte doubling time of <6 months (if initial ALC is ≥30,000/μL), OR

CONFIDENTIAL Page 32 of 61

Version: 1.0, Dated 12 September 2019

- e. Autoimmune anemia and/or thrombocytopenia that is poorly responsive to corticosteroids or other standard therapy, OR
- f. Constitutional symptoms, defined as any one or more of the following disease-related symptoms or signs occurring in the absence of evidence of infection:
 - i. Unintentional weight loss of $\geq 10\%$ within the previous 6 months, or
 - ii. Significant fatigue (> Grade 2), or
 - iii. Fevers >100.5°F or 38.0°C for ≥2 weeks, or
 - iv. Night sweats for >1 month.

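### The haemoglobin progression and stable-disease cells of protocol Table 6 do not meet, so a CLL-related fall of at least 2 g/dL but under 50% fits neither category

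*Protocol*

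**What the plan says.** Protocol section 8.2 gives the response criteria in Table 6.

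- **Haemoglobin, PD:** "Decrease of ≥ 50% over baseline secondary to CLL". The platelet PD cell directly above has identical wording.
- **Haemoglobin, SD:** a limited increase, or "decrease <2 g/dL".
- **Platelets, nodes, liver/spleen and lymphocytes, SD:** "Change of -49% to +49" per cent, each paired with a 50% PD limit.
- **Combination rules:** "For progressive disease, at least 1 of the criteria of group A or group B should be met"; "For stable disease, all of the criteria have to be met".
- **Standard:** "Disease assessment will be performed as per iwCLL guideline for CLL". The guideline's content is not reproduced beyond the table and its notes.

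Protocol section 6.5 bases the efficacy endpoints on response confirmed by the site investigator. The SAP repeats neither Table 6 nor any haemoglobin rule. It tabulates best overall response in four categories (10.5.4), counts SD in the disease control rate, DCR (10.5.1), and ends PFS and DoR at progression or death (10.5.5, 10.5.3). DoR is part of the primary objective.

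**The concern.** In every other percentage-based row of Table 6, PD begins where SD ends, apart from rounding between 49% and 50%. In the haemoglobin row SD stops at an absolute fall of 2 g/dL and PD starts only at a relative fall of 50%. A patient whose haemoglobin drops between those limits because of CLL, who meets no other PD criterion and does not qualify for CR or PR, cannot be classified by applying the table as printed. The site must improvise.

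The 50% limit is also hard to reach. It means 4.5 g/dL from a baseline of 9, or 6.5 g/dL from 13. Protocol section 5.2 says "Transfusions (blood/platelets) may be given, based on standard criteria and clinical judgment", so haemoglobin may be supported before it gets there. If the PD cell is the one in error, progression that shows first through haemoglobin would rarely be recorded, and PFS and DoR would run on to a later event or to censoring.

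**Working it through.** **Inputs.** PD limit: fall ≥50% (Table 6). SD limit: fall <2 g/dL (Table 6). Usual minimum baseline: 9 g/dL (protocol 4.1), with lower values admitted for marrow infiltration and no floor stated.

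**Design figure.** An exact two-stage binomial calculation (20 then 41 patients, stop at ≤8, reject at ≥31 of 61) gives power 0.904 at 60% and alpha 0.0487 at 40%. The stated 90% and 0.05 are reproduced. Nothing below depends on them.

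**Where the limits meet.** For baseline H, PD needs a fall of at least 0.5 × H. Setting 0.5 × H = 2 gives H = 4.0 g/dL. Above that, falls from 2 up to 0.5 × H satisfy neither cell.

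| Baseline (g/dL) | PD needs a fall of | Fall of 2 g/dL as % | Neither SD nor PD |
|---|---|---|---|
| 9 | ≥4.5 | 22% | 2 to <4.5 |
| 11 | ≥5.5 | 18% | 2 to <5.5 |
| 13 | ≥6.5 | 15% | 2 to <6.5 |
| 15 | ≥7.5 | 13% | 2 to <7.5 |

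So the gap exists at every baseline that meets the 9 g/dL criterion.

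**What else can trigger PD.** One criterion is enough, so nodes, liver/spleen, platelets and marrow remain available. Two routes are limited. The note to Table 6 excludes lymphocytosis alone. Marrow PD needs successive biopsies, whereas protocol 6.6 plans marrow sampling only at investigator discretion for eligibility, or to confirm CR.

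**Possible size.** The documents do not give the share of first progressions seen in haemoglobin alone. Call it s, and assume exponential PFS, a true median of 6 months, and that these events are never captured in any other way. The apparent median is then 6/(1 − s):

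- s = 0%: 6.0 months
- s = 2%: 6/0.98 = 6.1
- s = 5%: 6/0.95 = 6.3
- s = 10%: 6/0.90 = 6.7
- s = 20%: 6/0.80 = 7.5

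Both s and the 6-month median are assumptions. For each s the result is an upper bound, because another criterion or death would later record many of these patients.

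**The case against.** Most of the case against concerns how far the mismatch can be pushed, and most of it stands.

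- **Which cell is wrong.** A reader might infer that PFS and DoR are overstated. That requires the PD cell to be the error. The wording shared with the platelet cell suggests a copying slip but does not prove it, and the named guideline's content is not in the documents. If the SD cell is wrong, no progression is missed.
- **Delay to the next scan.** A reader might take the intervals between CT days 57, 113 and 197 (56 and 84 days) as the delay. Table 1 schedules a blood count at every treatment visit, and section 8.2 allows assessment when clinical progression is suspected. Nothing shows that another criterion would be met at exactly the next scan.
- **Inflated DCR.** This would need sites to record SD against the rule that all SD criteria be met. Read literally, a patient in the gap fails SD.
- **Section 6.2.3.** Its haemoglobin limit of 10 g/dL documents disease that warrants starting therapy. It is not an on-treatment progression threshold, so its difference from Table 6 is no contradiction.
- **Transfusion.** Table 2, footnote a, asks for haemoglobin to be measured before transfusion. This weakens the argument that transfusion masks falls, although earlier transfusions still have an effect.
- **Simply setting PD at the complement of SD.** That creates an overlap. From 13 g/dL or more, a fall of 2 can leave haemoglobin at or above 11.0 g/dL, which still satisfies the CR and PR cells. Under the printed PD cell such an overlap needs a baseline of 22. PD also leads to discontinuation (protocol 4.3, 6.7), so its threshold is not only an analysis choice.

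None of this closes the gap between the two cells. Deferring to the guideline and the investigator explains how a site might cope, but the plan's own table still gives no answer.

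**Conclusion.** The inconsistency is certain. At every baseline above 4.0 g/dL the haemoglobin PD and SD cells leave a range of falls unclassified, and the SAP has no rule for it.

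The effect on the endpoints is conditional. If the PD cell is wrong, the bias can only lengthen PFS and DoR or leave them unchanged; its size is unknown and may be zero. If the SD cell is wrong, the harm is confined to classification. That haemoglobin alone would rarely reach the printed PD limit is a fair inference from the values required, not a figure in the documents.

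The stakes are modest. SAP section 6 records 21 patients and no stage 2, DoR is summarised descriptively, and PFS is one single-arm Kaplan-Meier curve. The stage 1 responder rule and the design figures are unaffected. Counting more falls as progression could not add a responder, so it could not reverse a closure made for lack of response.

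**What to change.** 1. Reconcile the two haemoglobin cells with each other, with the CR and PR cells of the same row, and with the response standard the protocol names. This review does not say which threshold is right.
2. State the resulting rule in the SAP before database lock, including the category for a patient whose fall lies between the present limits.
3. From haemoglobin values already collected, list every fall of ≥2 g/dL but <50% that the investigator attributes to CLL, and flag those that stay at or above 11.0 g/dL.
4. Report PFS, DoR, best response and DCR with those falls counted as PD, as a sensitivity analysis only. Investigator-confirmed response stays the main analysis, and no treatment decision changes.

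The cost is a correction to the table, a short listing in 21 patients and one extra set of summaries. The drawbacks are that some falls must be attributed retrospectively, in an open-label study whose efficacy data have already been reviewed, and that PFS and DoR may come out slightly shorter in the sensitivity analysis.

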9 STATISTICAL METHOD AND CONSIDERATIONS

This section describes the statistical methods to be used to analyze efficacy and safety. These methods may be revised and updated due to reasons such as regulatory requirements or need for further clarifications. The final analysis plan will be documented in a formal statistical analysis plan (SAP) that must be finalized before database lock. The SAP will include details on how variables will be derived, how missing data will be handled, and how data will be presented as well as the details on statistical methods to be used for safety and efficacy analyses. The final clinical study report will discuss deviations from the SAP, if any.

9.1 **General Considerations**

Unless otherwise stated, all statistical analyses will be performed using a two-sided hypothesis test at the overall 5% level of significance. Continuous data will be described using the following descriptive statistics: n, mean, median, minimum and maximum. Data will be displayed in all listings sorted by phase, group and patient number.

When count data are presented, the percentage will be suppressed when the count is zero in order to draw attention to the non-zero counts. A row denoted "Missing" will be included in count tabulations where necessary to account for dropouts and missing values. Unless otherwise specified, the denominator for percentages will be the number of patients with a non-missing assessment in a given treatment group within the analysis population of interest.

All statistical analyses will be performed using SAS 9.1 or higher.

Determination of Sample Size

The sample size is derived based on Simon's two stage design to achieve 90% power at alpha of 0.05 for the null hypothesis of ORR \(\le 40\%,\) assuming 60\% response rate. Up to 61 patients will be enrolled. In stage 1, 20 patients will be enrolled, if 08 or fewer responders are observed in this stage, the study will be terminated without rejecting the null hypothesis. Otherwise, 41 additional

CONFIDENTIAL Page 50 of 61

^{*}Sum of the products of 6 or fewer lymph nodes (as evaluated by CT scans and physical examination). No increase in any lymph node and no new enlarged lymph node (diameter ≥ 1.5 cm). For small lymph nodes (longest diameter < 1.5cm), an increase <25% is not considered significant.

Version: 1.0, Dated 12 September 2019

patients will be enrolled into stage 2. If 31 or more responders are observed in the study, the null hypothesis of ORR \leq 40% will be rejected.

9.3 Study Population

The following 3 analysis populations are planned in the study.

- Modified Intent-to-Treat Population (mITT): the mITT is the primary efficacy analysis population and will include data from all patients who received at least 1 dose of study medication and provide at least 1 post-baseline efficacy assessment.
- Per-Protocol (PP) Population: the PP Population is a subset of the modified Intent-to-Treat Population and will include patients without major protocol deviations.
- Safety Population: Safety Population will include all subjects who receive at least 1 dose of the study drug.

Membership in the analysis populations will be determined before database lock.

9.4 Statistical Analysis

9.4.1 Demographic and baseline characteristics

Demographics and baseline characteristics will be summarized using descriptive statistics for continuous variables, and frequencies and percentages for categorical variables.

9.4.2 Safety analyses

The safety endpoints will include:

- Incidence of AEs and AEs considered to be drug-related
- Incidence of grade 3, grade 4 AEs
- Incidence of SAEs and death
- Laboratory values
- ECG/vital signs

The safety endpoints will be listed and/or summarized. No inferential statistical analyses will be performed.

The analyses of safety will be based on the frequency of adverse events and their severity for patients in each portion who received at least one dose of study treatment. Worst toxicity grades per patient will be tabulated for select adverse events and laboratory measurements by using NCI CTCAE criteria v5.0 with exceptions for platelet, hemoglobin and ANC that are recommended by iwCLL guidelines for the CLL.

9.4.3 Efficacy analyses

The efficacy endpoints will include:

- Objective Response Rate
- Duration of response
- Progression free survival (PFS)

The analysis will be done as per the disease subtypes and overall. Additional analyses (e.g. CR rates) may also be performed as appropriate. These analyses will be performed from time to time for presentation/publication purposes.

CONFIDENTIAL Page 51 of 61

Version: 1.0, Dated 12 September 2019

10 ETHICAL, FINANCIAL, AND REGULATORY CONSIDERATIONS

This trial will be conducted according to the standards of Good Clinical Practice outlined in the ICH E6 Tripartite Guideline, World Medical Association's Declaration of Helsinki, local regulatory requirement(s), institutional research policies and procedures.

All potential serious breaches must be reported to Rhizen immediately. A serious breach is a breach of the conditions and principles of GCP in connection with the study or the protocol, which is likely to affect, to a significant degree, the safety or physical or mental integrity of the subjects of the study or the scientific value of the study.

